4.5 Responsibilities

Principal Investigator (PI):

Checking for AEs when participants are reviewed or followed-up.

1. Using medical judgement in assigning seriousness and causality

2. Ensuring that all SAEs are recorded and reported to the Sponsor within 24 hours of becoming aware of the event and provide further follow-up information as soon as available. Ensuring that SAEs are chased with Sponsor if a record of receipt is not received within 2 working days of initial reporting.
3. Ensuring that AEs are recorded and reported to the Sponsor in line with the requirements of the protocol.

Chief Investigator (CI) / delegate or independent clinical reviewer:

1. Clinical oversight of the safety of patients participating in the trial, including an ongoing review of the risk / benefit.
2. Immediate review of all SAEs
3. Review of specific SAEs in accordance with the trial risk assessment and protocol as detailed in the Trial Monitoring Plan.
4. Production and submission of annual reports to the relevant REC.

Sponsor or delegate (WCTU):

1. Central data collection and verification of AEs, and SAEs, according to the trial protocol.
2. Expectedness assessment of related SAEs
3. Reporting safety information to the CI, delegate or independent clinical reviewer for the ongoing assessment of the risk / benefit according to the Trial Monitoring Plan.
4. Reporting safety information to the independent oversight committees identified for the trial (Data Monitoring Committee (DMC) and / or Trial Steering Committee (TSC)) according to the Trial Monitoring Plan.
5. Expedited reporting of related and unexpected SAEs to the REC within required timelines.
6. Notifying Investigators of related and unexpected SAEs that occur within the trial.

Trial Steering Committee (TSC):

In accordance with the Terms of Reference for the TSC, periodically reviewing safety data and liaising with the DMC regarding safety issues.

Data Monitoring Committee (DMC):

In accordance with the Terms of Reference for the DMC, periodically reviewing unblinded overall safety data to determine patterns and trends of events, or to identify safety issues, which would not be apparent on an individual case basis.

4.6 Notification of deaths

Death is collected as a trial outcome and will be captured using the trial CRF.

4.7 Reporting urgent safety measures

If any urgent safety measures are taken the CI/Sponsor shall immediately and in any event no later than 3 days from the date the measures are taken, give written notice to the relevant REC of the measures taken and the circumstances giving rise to those measures.

5. DATA MANAGEMENT

Personal data collected during the trial will be handled and stored in accordance with UK GDPR and Warwick SOPs.

Personal identifiable data will be held separately to trial data within the trial database, with linkage provided through a unique trial number.

Source documents are where data are first recorded, and from which participants' CRF data are obtained. These include, but are not limited to, hospital records (from which medical history and previous and concurrent medication may be summarised into the CRF), clinical and office charts, laboratory and pharmacy records, diaries, microfiches, radiographs, and correspondence.

CRF entries will be considered source data if the CRF is the site of the original recording (e.g. there is no other written or electronic record of data). All documents will be stored safely in confidential conditions. On all trial-specific documents, other than the signed consent, the participant will be referred to by the trial participant number/code, not by name.

5.1 Data management

Case Report Forms (CRFs) and a Progressive Web Application (PWA) will be developed to collect all required trial data. Where applicable, a random sample of at least 10% of CRFs will be checked, by the trial Research Team, against entries within the database and the source data for quality purposes. The percentage checked will be increased if a significant error rate is found. In addition, the first set of recruitment data collected from all new sites will be scrutinised.

5.1.1 Participant enrolment

The randomisation PWA will collect data relating to the management of the traumatic injuries sustained, the hospital the participant was taken to and participant characteristics. Local research teams, at the hospital the ambulance service delivers the participant to, will locate and follow-up the participant as appropriate.

5.1.2 In hospital through to discharge

For participants admitted to hospital a small amount of data will be collected on admission (FIM, ASIA neurological scale, analgesia given) by the local research team and at the point of hospital discharge. Data will be recorded using standardised case report forms (CRFs). Health-related quality of life will be collected using the EQ-5D-5L/EQ-5D-Y completed by the participant or, if they lack capacity, their consultee. The local research teams will be responsible for collecting this data.

At discharge FIM (completed by the appropriately trained clinical or research staff member), length of hospital stay, further treatment for spinal injury, discharge destination, and safety outcomes will be collected by the local research teams from the participant's medical records on the standardised trial CRFs. In addition, participants will also be asked to complete an EQ-5D-5L/EQ-5D-Y at discharge.

5.1.3 Follow-up

Survival status will be collected by hospital/Imperial research staff for all participants at 30, 90 and 180 days.

Following confirmation of survival status, participants will be followed up at 30 and 180 days and asked to complete two questionnaires. The participant may opt to complete these questionnaires by post, online or by telephone according to their preferences.

If the participant lacks capacity then a consultee may complete the questionnaires on their behalf. If the participant or consultee cannot be reached after 3 contact attempts no further attempts will be made on that occasion, however if they do not respond after 3 contact attempts at 30 days a further contact will be made (on up to 3 occasions) at 180 days.

For patients who have been discharged, a tele-video clinic or out-patient follow-up visit will be arranged for the patients (180 days post-randomisation) with the Imperial research team, where the FIM score will be documented, along with cost and resource utilisation and health-related quality of life (EQ-5D-5L/EQ-5D-Y). If the patient is still in hospital, a member of the local research team will aim to obtain their data by visiting them and if required, assisting them with the completion of this questionnaire.

To ensure accurate, complete and reliable data are collected the trial management team at WCTU and/or Imperial College London will provide training to site staff in the format of investigator meetings and site initiation visits. Quality assurance procedures will be put in place to ensure training is delivered in a standardised manner. The trial management team will provide the local Principal Investigators and research staff with training on the protocol, completion of the CRF and trial procedures including standard operating procedures.

5.2 Database

The trial database will be developed by the Programming Team at WCTU and all specifications (i.e. database variables, validation checks, screens) will be agreed between the programmer and appropriate trial staff.

5.3 Data storage

All essential documentation and trial records will be stored by WCTU and recruiting sites in conformance with the applicable regulatory requirements and access to stored information will be restricted to authorised personnel.

5.4 Data access and quality assurance

All data access will be controlled by individual usernames and passwords and any changes to data will require the user to enter their username and password as an electronic signature in accordance with regulatory requirements. Staff will have access restricted to the functionality and data that are appropriate for their role and responsibilities in the trial, which is documented on the central coordinating delegation log. Any data that are transferred out of the secure environment (for example for statistical analysis) will adhere to Warwick SOPs.

5.5 Data Shared with Third Parties

As of 1 July 2018, manuscripts submitted to ICMJE journals that report the results of clinical trials must contain a data sharing statement as described below.

Clinical trials that begin enrolling participants on or after 1 January 2019 must include a data sharing plan in the trial's registration. The ICMJE's policy regarding trial registration is explained at www.icmje.org/recommendations/browse/publishing-and-editorial-issues/clinical-trial-registration.html. If the data sharing plan changes after registration this should be reflected in the statement submitted and published with the manuscript and updated in the registry record.

Full details of what should be included: <http://www.bmj.com/content/357/bmj.j2372>

Further guidance:

Good Practice Principles for Sharing Individual Participant Data from Publicly Funded Clinical Trials (Version 1)

<http://www.methodologyhubs.mrc.ac.uk/files/7114/3682/3831/Datasharingguidance2015.pdf>

The trial statisticians and DMC will have access to the dataset for the analysis of trial outcomes. Once the main analyses have been undertaken, de-identified individual participant data will be available to other investigators subject to approval of data analysis plans and compliance with the University of Warwick SOPs on Data Management and Sharing. Approval of data analysis plans will be the responsibility of the TSC during the lifetime of the trial. Following study completion, the Chief Investigator and WCTU Data Sharing Committee will be jointly responsible for the approval of requests for data from other researchers. Approval will only be provided for proposals which are scientifically sound and have ethical approval. Data sharing agreements will be put in place for any sharing of the trial data. The trial will comply with Data Sharing Policies that may be instituted by the NIHR during the lifetime of the project.

5.6 Archiving

Trial documentation and data will be archived for at least ten years after completion of the trial in accordance with Sponsor guidelines.

6. STATISTICAL ANALYSIS

6.1 Power and sample size

The planned size of this trial is 8316 patients (4158 per arm). The sample size is based on a non-inferiority hypothesis, where our objectives are to demonstrate that the movement minimisation (intervention) is no worse than triple immobilisation (comparator), by a pre-specified small difference, δ , on the functional outcome (FIM-motor) score. Statistically, our null hypothesis is that the intervention is inferior to the comparator by δ , and the alternative is that the intervention is non-inferior to the comparator by amount δ . Choosing δ as 2 points on the FIM-motor, as the difference that is clinically acceptable as a margin of non-inferiority between the interventions, then using a standard deviation of 25.93, 90% power and two-sided 5% significance level (with loss-to-follow-up rate of 15%), we would require a total sample of 8316 patients. The sample size was informed using the following parameters:

1. Non-inferiority margin: Regulatory guidelines recommend defining the margin based on a review of historical evidence of the efficacy of the comparator^{19,20}. The minimal clinically important difference (MCID) for the FIM-motor is not established for the spinal cord injury patients²¹. However, using data from acute stroke patients, the MCID = 22 points (for FIM total), 17 points (for FIM-motor) and 3 points (for FIM-cognition) subscale²². This would suggest that a MCID for the FIM-motor (over the total or subscale scores) can be taken to be at least 3 points. Thus a 2-point difference on the FIM-motor scale, can be considered as a

viable non-inferiority margin. This equates to an effect size of 0.1, which using Cohen's criteria²³ would be below what is classed as a 'small' effect size usually specified for superiority studies.

2. Type 1 error: Using regulatory guidance from the EMA CHMP26 we specify a two-sided 0.05 level of significance (or one-sided 0.025). An alternative way of stating this requirement is that the lower bound of the two-sided 95% confidence interval (or one-sided 97.5% interval) for the difference between active and placebo should be above zero.
3. Standard deviation: A study conducted in 2 adult major (level 1) trauma centres in Victoria, Australia (243 patients) provided the baseline data of FIM-motor in adults with a blunt mechanism of injury and an Injury Severity Score (ISS) on admission to the hospital of >15 ²⁴. This population is expected to closely resemble the population that will be included in our trial. This study found the median (IQR) for the FIM-motor to be 61 (44-79) at discharge. Using a conversion formula²⁵, we derive the standard deviation of 25.93 from these data. In another prospective study carried out in Australia, data was analysed on an in-patient rehabilitation of spinal cord injury group (no. of episodes= 3753) from 2003- 2012²⁶. The FMI-motor median (and IQR) at discharge was 76 (51-83), which equates to a standard deviation of 23.7. Thus, there is evidence that a standard deviation with the range of 24-26 is a reliable estimate.
4. Loss-to-follow up rate: Using the TARN data approximately 10% of patients die prior to hospital discharge. The LTFU rate is generously set at 15% (10% death; 5% loss of primary outcome data at discharge) but we anticipate that it will be much lower, in keeping with the recently published CRASH-3 trial, which had a $< 2\%$ LTFU rate with a similar population and outcome assessment at discharge.

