2.3.1 Effectiveness

Primary effectiveness outcome:

- Total Functional Independence Measurement motor (FIM-motor) score at discharge. The FIM is an 18-item instrument measuring a person's level of disability in terms of burden of care. The FIM should be rated by the consensus opinion of a multidisciplinary team, but the evaluation is often performed by a single professional.

Secondary effectiveness outcomes:

- FIM-motor at 30 days, 180 days after randomisation at video clinic or follow up appointment;
- FIM-total and cognition scales at discharge, 30 days and 180-day at video clinic or follow up appointment;
- ASIA Impairment Scale at discharge;
- Mortality (at days 30, 90 and 180);
- Intervention for c-spine injury in the first 30 days or discharge (use of collar for > 2 weeks, halo brace, c-spine surgery);
- Discharge destination;
- Pre-hospital analgesic requirements (from Ambulance PRF).

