2.8 Randomisation

2.8.1 Randomisation

Patients will be randomised on scene by the recruiting paramedic/ambulance service practitioner. A progressive web application (PWA) will be developed for randomisation. The PWA will confirm participant was eligible for immobilisation as per JRCALC guidelines prior to randomising with automatic date/time/location stamping and site and confirmation of age group (<16 and ≥ 16 years). The PWA will be developed by the Programming Team in Warwick and tested in the pilot phase.

Patients will be randomised in a ratio of 1:1 (movement minimisation: triple immobilisation) and stratified by clinical factors such as age group (<16 and ≥ 16 years) and recruiting centre to ensure balance over the two intervention arms.

If the PWA system is unavailable, a remote randomisation system will be provided by WCTU/Imperial College. The remote randomisation telephone number will be provided to ambulance services in the Investigator Site Files.

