6.2 Statistical analysis of efficacy and harms

6.2.1 Primary outcome analysis

For the primary analysis, the difference in the FIM-motor score (and 95%) confidence interval will be derived using unadjusted and adjusted (for important covariates) analyses, using the linear regression models. In terms of interpretation, the intervention would be said to be not unacceptably worse than (i.e., non-inferior to) the control if, when the 95% CI around the difference in the effect size between the interventions is calculated and the lower bound of the interval does not extend beyond the -2.

A further exploratory analysis to assess the impact of missing outcome data on FIM-motor score will be examined using multiple imputation techniques.

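### Deaths before discharge are planned as loss to follow-up, so the primary non-inferiority test is in effect a comparison of survivors, and excess deaths in either arm do not count against that arm

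*Protocol*

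**What the plan says.** The primary outcome in Protocol section 2.3.1 is "Total Functional Independence Measurement motor (FIM-motor) score at discharge". Section 2.3 gives the scale as 13 to 91, with no value for a participant who dies.

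In section 6.1, item 4 expects deaths before discharge in about one patient in ten: "Using the TARN data approximately 10% of patients die prior to hospital discharge". It places them inside the loss allowance: "The LTFU rate is generously set at 15% (10% death; 5% loss of primary outcome data at discharge". The margin is set in the same section: "Choosing δ as 2 points on the FIM-motor".

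Section 6.2.1 estimates the difference by linear regression, unadjusted and adjusted, and concludes non-inferiority if the lower 95% limit does not pass -2. Its only provision for absent scores is this: "A further exploratory analysis to assess the impact of missing outcome data on FIM-motor score will be examined using multiple imputation techniques". It gives no rule for death.

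Mortality at 30, 90 and 180 days is a separate secondary outcome (section 2.3.1), with no margin and no stated role in the non-inferiority claim. By contrast, section 3.2.2 does assign a score where none was measured: participants who leave the emergency department before assessment are recorded as totally independent.

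**The concern.** A discharge score does not exist for someone who dies in hospital. Death could be affected by allocation, so leaving the dead out means the groups compared are no longer the groups randomised.

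In a non-inferiority trial this bears directly on the claim. The protocol could report movement minimisation as not unacceptably worse on the primary outcome while more of its patients died, because those deaths do not enter the estimate. If the extra deaths fell on patients who would have scored low, the surviving group would look better than it should. The same mechanism would favour the control arm if the excess were there.

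**Working it through.** **Inputs from the protocol.** Margin 2, SD 25.93, 90% power, one-sided 0.025 and 15% loss (section 6.1); 1:1 allocation (section 2.8.1); 10% deaths and 5% other loss (section 6.1, item 4); median discharge FIM-motor 61 in the first source and 76 in the second (section 6.1, item 3); scale floor 13 (section 2.3).

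**Assumptions.** The median of 61 (or 76) stands in for the survivor mean, survivor SD is 25.93, and death is scored 13. The protocol states none of these.

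**1. The plan's own sample size.** Evaluable per arm = 2 × [25.93 × (1.960 + 1.282) / 2]² ≈ 3,533, or 3,534 with the noncentral t. Then 3,534 / 0.85 = 4,157.6, rounded up to 4,158 per arm and 8,316 in total, exactly as stated. If only the 5% of other loss were allowed for, 3,533 / 0.95 gives 3,719 per arm and 7,438 in total. So the stated figure treats the dead as supplying no score.

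**2. Excess mortality equal to the margin.** With survivors alike in both arms, an excess d shifts the death-inclusive mean by -d × (61 - 13) = -48d. Setting this to -2 gives d = 2/48 = 4.2 percentage points. This does not depend on the control death rate.

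**3. Chance of declaring non-inferiority.** Control mortality 10%, survivors alike, 4,158 per arm.
- Deaths left out: Φ(2/SE - 1.96), with SE = 25.93 × √(1/n₁ + 1/n₂), n₁ = 4,158 × 0.85 and n₂ = 4,158 × (0.85 - d).
- Deaths scored 13: Φ((2 - 48d)/SE - 1.96), with per-arm variance (1-p) × 25.93² + p(1-p) × 48², where p is the arm's death rate, and n = 0.95 × 4,158 = 3,950.

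| Excess deaths on movement minimisation | Extra deaths | Deaths left out | Deaths scored 13 |
|---|---|---|---|
| 0 | 0 | 90.0% | 87.7% |
| +2 points | 83 | 89.7% | 36.3% |
| +4 points | 166 | 89.3% | 3.3% |
| +5 points | 208 | 89.1% | 0.5% |

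**4. If the extra deaths are would-be low scorers.** At +2 points, the survivor mean in the arm with the excess is (0.90 × 61 - 0.02f)/0.88, where f is the score they would have had. For f = 13 this is 62.09 (+1.1); for f = 44 it is 61.39 (+0.4).
- Excess on movement minimisation: the chance of declaring non-inferiority rises to 99.9% (f = 13) or 97.0% (f = 44).
- Same excess on triple immobilisation: the difference changes sign. With SE 0.621, Φ((2 - 1.09)/0.621 - 1.96) is about 31%, and Φ((2 - 0.39)/0.621 - 1.96) is about 74%.

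**5. Power of a death-inclusive analysis at 8,316.** With mean 61, variance = 0.9 × 25.93² + 0.09 × 48² = 812.5, so SD = 28.5 and SE = 28.5 × √(2/3,950) = 0.641. Power = Φ(2/0.641 - 1.96) = 87.7%. With mean 76 and the same survivor SD, the gap is 63, SD = 31.0 and power = 81.7%. Restoring 90% would need 8,988 or 10,646 participants respectively.

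**The case against.** Much of the case on the other side stands, and it limits what may be claimed.

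- **A reader might infer that the protocol prescribes a survivor-only analysis.** It does not say so. The exclusion follows from the sample-size arithmetic. Section 6.2.1 is silent, and a detailed statistical analysis plan is promised in section 6.2.2. But a plan that gave the dead a score would change the estimand, the SD and the power fixed in section 6.1.
- **A reader might infer that the bias always runs in the unsafe direction.** It depends on which arm has the excess and in whom. Section 1.3 raises possible harm from triple immobilisation, and step 4 shows that excess deaths there would work against movement minimisation.
- **A reader might infer that imputation would give the dead a discharge score.** That is one reading. Section 6.1 separates death from the 5% loss of outcome data, and the imputation may be meant for the latter only. The text does not settle it.
- **A reader might infer that excess deaths would go unnoticed.** They would not. Mortality is a secondary outcome, and the Data Monitoring Committee reviews safety data and interim outcomes (section 7.10). An excess of 4.2 points is 0.042 × 4,158, or about 175 deaths, with z about 5.9. An excess of 2 points would be detected with about 83% power. But nothing makes the non-inferiority claim depend on that result.
- **The 10% may be high.** Section 6.1 expects the overall loss to be much lower than 15%, and section 2.7.5 expects high survival. Fewer deaths shrink the problem without removing it.
- **A composite has its own hazard.** It can mask worse function. If survivors on movement minimisation score 3 points lower but mortality there is 8% rather than 10%, the composite difference is -3 × 0.92 + 0.02 × 48 = -1.8. This argues for showing the survivor analysis as well, and against insisting that the composite become the primary analysis.

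**Conclusion.** The point holds in this form. Section 6.1 plans the expected deaths as loss, section 6.2.1 gives death no place in the test, and the primary comparison is therefore in effect among survivors. Excess deaths in an arm cannot lower that arm's estimate and may raise it. Movement minimisation could be declared non-inferior despite excess mortality, which would be visible only outside the primary test.

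With survivors alike, 5 points of excess mortality move the chance of success only from 90.0% to 89.1%. With death scored 13 and survivor mean 61, 4.2 points use up the whole margin. These sizes rest on the assumed score for death, the median standing in for the mean, and 10% control mortality. The structural point rests on none of them.

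**What to change.** - **Section 6.2.1, analysis:** pre-specify a death-inclusive analysis of all randomised participants, for example death before discharge at the scale floor of 13, or a rank-based equivalent with its own criterion. Report it beside mortality by arm and the survivor analysis.
- **Section 6.2.1, claim:** claim non-inferiority only if the death-inclusive result also meets the -2 criterion.
- **Section 6.2.1, imputation:** limit multiple imputation to survivors with no score.
- **Section 6.1:** list deaths separately from loss to follow-up, and state the power of the death-inclusive analysis.

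**Cost.** Wording in the protocol and the analysis plan. No new data are needed, since section 4.6 already captures death on the case report form. At 8,316 the death-inclusive analysis has about 88% power with survivor mean 61 and about 82% with 76, a loss of roughly 2 to 8 percentage points. The chance of meeting both criteria can be no higher than that. This should be stated rather than met by enrolling more. Whether the composite should replace the primary analysis is for the sponsor to decide.
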